ELIGIBILITY: (children)	Inclusion criteria: 
1. Patients aged one to five years old presenting either to primary care or to the emergency department or to secondary care (e.g., outpatients) or identified from primary care records and have been diagnosed with wheezing by their GP or paediatrician who has decided to prescribe any bronchodilator, ICS or montelukast on clinical grounds2. Parents/Carers able to understand and familiarize themselves with the study and are willing to provide informed consent Exclusion criteria: 
1. Inability to understand and cooperate with study procedures2. Significant co-morbidity (respiratory or otherwise), for example cystic fibrosis (excluding atopic disorders such as eczema, allergic rhinitis and food allergy)3. Withholding or withdrawal of informed consent4. Severe procedural anxiety (needle phobia)5. Child is already enrolled in another study involving investigational medicinal product (CTIMP)6. History of anaphylaxis or near-fatal asthma that resulted in intubation / assisted ventilation.
ELIGIBILITY: (Healthcare professionals)	Inclusion Criteria: 
1. Doctors and nurses working in GP practices. Exclusion Criteria: 
1. Inability to understand and cooperate with study procedures.

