6. STUDY DESIGN

This is a pragmatic, observational study involving preschool children with wheeze aged one to five years old. All treatment and routine monitoring decisions will be at the discretion of their treating general practitioner (GP) or paediatrician (as per usual clinical practice), blinded to the study measurements. After clinical consultation and following submission of the electronic informed consent through the Qualtrics® platform (offered by Imperial College London), the parent/carer will be asked to give the contact details of the child's GP or paediatrician, who will be informed about child's participation in this study through a letter sent to his/her email along with the patient information sheet. The parent carer will be then shown a standard video questionnaire and will be asked to identify what respiratory sounds their children have been making. The child will be booked for the three biomarker tests [atopic sensitisation, blood eosinophil count and FeNO (off-line method)]. The tests will be carried out once and at a time of clinical stability. In this visit, a sample of the child's exhaled tidal breath will be collected in a suitable bag in duplicate for offline measurement of FeNO later on with chemiluminescence. Skin prick tests will be performed to: (a) house dust mite, (b) grass pollen, (c) tree pollen, (d) cat hair(e) dog hair, as well as normal saline and histamine and these will be applied on either the child's back, leg or arm. If the child has been prescribed antihistamines, we will ask for these to be withheld for 72 hours prior to skin prick testing. FeNO values (offline method) ≥ 10 ppb will indicate Type 2 inflammation and wheal diameter, measured with a specialised skin prick test ruler, ≥ 3 mm will indicate sensitisation to the applied aeroallergen. In addition, skin prick tests will allow the assessment of which aeroallergen is the most useful predictor of outcomes in preschool children. Finally, the peripheral blood eosinophil count will be measured from a finger prick blood sample, using the Haemocue machine, allowing a result in approximately 2 minutes. Values ≥ 300 cells/ μ l indicate Type 2 inflammation. All tests will normally take no more than one hour.

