The recruitment period will approximately last 9 months, and all preschool wheezers can join the study at any point (Appendix 1: Recruitment Plan). Parents/Carers of preschool children presenting to primary care or to the Emergency Department (ED) or to secondary care (e.g., outpatients) as well as those identified from primary care records and who have been diagnosed by a GP or paediatrician with wheezing, will be approached by collaborating doctors and nurses who will ask their parents if they are willing to have their child participate in the study (Appendix 1: Recruitment Plan). A patient information sheet will be given, containing all the information regarding the project and the contact details of the research team, for further questions. They will be asked for their willingness to give the study team permission to contact them and discuss recruitment, and if so, they will submit their contact details in an electronic form made with Qualtrics® questionnaire platform (offered by Imperial College London), which allows gathering data according to the GCP guidelines and as used for years in the Breathing Together study (19). This form will be available online in the Asthma UK Centre for Applied Research's (AUKCAR) website. The initial introduction

will be made either by the clinical team (above) with the study team contacting them at a later date to give more information or by [name] if he is there in person.

Additionally, the Emergency Department of Oxford Universities Hospital (OUH) Trust will identify patients who have previously presented and diagnosed with wheezing in the Emergency Department. A regular search of the OUH databases will be performed by the clinical care team to identify patients who meet the eligibility criteria and have attended the Emergency Department. Parents/carers of eligible participants will be informed about the study by phone by a member of their clinical care team and asked whether they agree to be contacted by the study team to give them more information and send them the participant information sheet. Their contact details will be then submitted in the TAILOR study contact details form.

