7. CHILD PARTICIPANT ENTRY

7.1. PRE-REGISTRATION EVALUATIONS AND RECRUITMENT

This is a pragmatic, observational study involving preschool children with wheeze aged one to five years old. All treatment and routine monitoring decisions will be at the discretion of their treating general practitioner (GP) or paediatrician (as per usual clinical practice), blinded to the study measurements. After clinical consultation and following submission of the electronic informed consent through the Qualtrics® questionnaire platform (offered by Imperial College London), the parent/carer will be asked to give the contact details of the child's GP or paediatrician, who will be informed about child's participation in this study through a letter sent to his/her email along with the patient information sheet. The parent carer will be then shown a standard video questionnaire and will be asked to identify what respiratory sounds their children have been making. The child will be booked for the three biomarker tests [atopic sensitisation, blood eosinophil count and FeNO (off-line method)]. The tests will be carried out once and at a time of clinical stability. In this visit, a sample of the child's exhaled tidal breath will be collected in a suitable bag in duplicate for offline

measurement of FeNO later on with chemiluminescence. Skin prick tests will be performed to: (a) house dust mite, (b) grass pollen, (c) tree pollen, (d) cat hair, (e) dog hair, as well as normal saline and histamine and these will be applied on either the child's back, leg or arm. If the child has been prescribed antihistamines, we will ask for these to be withheld for 72 hours prior to skin prick testing. FeNO values (offline method) ≥ 10 ppb will indicate Type 2 inflammation and wheal diameter, measured with a specialised skin prick test ruler, ≥ 3 mm will indicate sensitisation to the applied aeroallergen. In addition, skin prick tests will allow the assessment of which aeroallergen is the most useful predictor of outcomes in preschool children. Finally, the peripheral blood eosinophil count will be measured from a finger prick blood sample, using the Haemocue machine, allowing a result in approximately 2 minutes. Values ≥ 300 cells/ μ l indicate Type 2 inflammation. All tests will normally take no more than one hour.

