All recruitment procedures will be in accord with the GCP, and parents/carers will be given detailed information regarding the study as well as all the time they need to understand it. Parents/guardians have at least 24 hours to consider participation. Recruitment will only commence after parents/carers have fully understood the project and submitted the electronic informed consent form through the Qualtrics® platform (offered by Imperial College London).

Child participants entering the study upon their parents' wish, will be fully screened by the Principal Investigator (PI) or someone else from the research team who is suitably qualified and delegated to do so, with the latter taking informed consent as well. After the electronic informed consent sheet is submitted, parents will be asked to provide the contact details of their child's GP or paediatrician, to inform him/her about the child's participation in this study through a letter sent by email along with this patient information sheet. In addition, we will ask them to provide some of the child's personal data (Appendix 1: Recruitment Plan, Table 3: The personal data that will be obtained by each individual participant). Children's full name, date of birth, gender, ethnicity as well as, their parent's full name, telephone number and email address will be added in the child's patient card. All other data obtained from the study will be added in the Case Report Form (CRF).

Follow-up: We will arrange for a short monthly electronic questionnaire to be sent by email to the parents/carers, in order to record on a monthly basis, the days their child was out of childcare, days the carer missed from work, unscheduled health care visits and use of rescue therapy or oral corticosteroids (including dosage) (Appendix 4: Monthly Questionnaire). In addition, we will record the children's TRACK™ score (Test for Respiratory and Asthma Control in Kids) (Appendix 3: TRACK™ score questionnaire) every 3 months, to assess wheeze control. The questionnaires will be made and sent through the Qualtrics® questionnaire platform (offered by Imperial College London). There will be review visits every 3 months, to evaluate their progression in person, but if not feasible, video calls will be arranged through Microsoft Teams. Correct use of spacers will be ensured after guiding parents on how to use them and will be done by their GP or paediatrician as well as from [name] who is a registered pharmacist in the UK.

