7.2. INCLUSION AND EXCLUSION CRITERIA

7.2.1. CHILDREN

INCLUSION CRITERIA	EXCLUSION CRITERIA

1. Patients aged one to five years old presenting to primary care or to the emergency department or to secondary care (e.g., outpatients) or identified from primary care records and have been diagnosed with wheezing by their GP or paediatrician who has decided to prescribe any bronchodilator, ICS or montelukast on clinical grounds
	
1. Inability to understand and cooperate with study procedures
 
2. Significant co-morbidity (respiratory or otherwise), for example cystic fibrosis (excluding atopic disorders such as eczema, allergic rhinitis and food allergy)
 
3. Withholding or withdrawal of informed consent

2. Parents/Carers able to understand and familiarize themselves with the study and are willing to provide informed consent
	
4. Severe procedural anxiety (needle phobia)
 
5. Child is already enrolled in another study involving investigational medicinal product (CTIMP)
 
6. History of near-fatal asthma that resulted in intubation / assisted ventilation.

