19. APPENDICES

19.1. APPENDIX 1: RECRUITMENT PLAN

The recruitment period will approximately last 9 months, and all preschool wheezers can join the study at any point. Parents/Carers of preschool children presenting to primary care or to the Emergency Department (ED) or to secondary care (e.g., outpatients) as well as those identified from primary care records and who have been diagnosed by a GP or paediatrician with wheezing, will be approached by collaborating doctors and nurses who will ask their parents if they are willing to have their child participate in the study. The list of recruitment sites is given below (Table 1). A patient information sheet will be given, containing all the information regarding the project and the contact details of the research team, for further questions. They will be asked for their willingness to give the study team permission to contact them and discuss recruitment, and if so, they will submit their contact details in an electronic form made with the Qualtrics® questionnaire platform (offered by Imperial College London), which allows gathering data according to the GCP guidelines and as used for years in the Breathing Together study (19). Additionally, the questionnaire form submission will not collect parents' IP address or geolocation. This form will be available online in the Asthma UK Centre for Applied Research's (AUKCAR) website. The initial introduction will be made either by the clinical team (above) with the study team contacting them later to give more information or by [name] if he is there in person.

Name of Participating NHS Organisation	University of Oxford NHS Hospitals
Location	Activity
Oxford University Hospitals NHS Foundation Trust	Participant Identification, Review Visits, Biomarker testing (finger prick test, skin prick test, collection of FeNO in a bag) Participant Identification
John Radcliffe Hospital	
Oxfordshire Clinical Commissioning Group	
Bicester Health Centre	
White Horse Medical Practice	
Oxfordshire BCSC (Horton Hospital)	
Whitchurch Surgery	
Norden House Surgery	
The Swan Practice	
Windrush Surgery	
CRN East Midlands	

Table 1. Patient identification and recruitment sites

Study procedures	Eligibility assessment	Before starting the study
Child participant identification	X	
Contact information submission	X	
Telephone/email contact with parents	X	
Inclusion/Exclusion criteria		X
Patient Information Sheet		X
Face-to-face project discussion		X
Electronic Informed Consent		X

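### Child exclusion 6 names anaphylaxis in the Study Summary but not in Section 7.2.1, and the Summary leaves the reach of its ventilation qualifier unclear

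*Combined protocol and SAP*

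**What the plan says.** Eligibility for children is set out in the Study Summary (Section 2) and again in Section 7.2.1. Each list has six exclusions.

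- Study Summary, exclusion 6: "History of anaphylaxis or near-fatal asthma that resulted in intubation / assisted ventilation".
- Section 7.2.1, exclusion 6: "History of near-fatal asthma that resulted in intubation / assisted ventilation".

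The only other criterion that might bear on a history of anaphylaxis is exclusion 2, significant co-morbidity. It does not name anaphylaxis, and in both lists it carries a carve-out: "excluding atopic disorders such as eczema, allergic rhinitis and food allergy".

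Three places apply the criteria without saying which list is meant:

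- Section 6, on Emergency Department records: "A regular search of the OUH databases will be performed by the clinical care team to identify patients who meet the eligibility criteria".
- Section 7.1, on children entering the study, who "will be fully screened by the Principal Investigator (PI) or someone else from the research team who is suitably qualified".
- Appendix 1, whose procedures table has a row for "Inclusion/Exclusion criteria", ticked under the step before the study starts.

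The procedure at issue is described in Section 7.1: "Skin prick tests will be performed to: (a) house dust mite, (b) grass pollen, (c) tree pollen, (d) cat hair, (e) dog hair". It is planned for every child at the first testing visit, with an optional repeat of the biomarker tests three months later.

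**The concern.** Both lists are current text, and each is written as an operative rule. If they differ, two screeners can each follow the protocol and reach opposite decisions on the same child. An auditor would then have no basis for calling the enrolment compliant or not.

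The criterion concerned is relevant to safety. Sections 5.1 and 8.7 identify allergic reaction as a risk of the study procedures and provide for it, and Section 5.1 includes a figure on anaphylaxis after skin prick testing. Whether a past anaphylaxis bars entry should therefore have one clear answer.

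**Working it through.** There is no figure to reproduce, so the check is a comparison of wording.

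**Step 1: the two lists, item by item.** Exclusions 1 to 5 match. Exclusion 6 differs by the words naming anaphylaxis, which are in the Summary and absent from Section 7.2.1. That is 1 item of 6. Both versions are complete sentences, so neither redaction nor a PDF-reading fault is a plausible explanation.

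**Step 2: does another criterion close the gap?** Exclusion 2 gives a screener some discretion, but it does not name anaphylaxis and it removes food allergy from its own scope. It is not a rule that settles the matter.

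**Step 3: the Summary's grammar.** The closing clause on intubation or assisted ventilation can attach to near-fatal asthma only (broad reading: any past anaphylaxis excludes) or to both conditions (narrow reading: only ventilated anaphylaxis excludes).

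**Step 4: what each reading does.** Take two hypothetical children, neither with near-fatal asthma, and apply exclusion 6 alone.

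| Child | Summary, broad | Summary, narrow | Section 7.2.1 |
|---|---|---|---|
| A: past anaphylaxis, not ventilated | excluded | not excluded | not excluded |
| B: past anaphylaxis, ventilated | excluded | excluded | not excluded |

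Child A is excluded under 1 of 3 readings and child B under 2 of 3. These counts show where the wording leaves the answer open. They do not measure how often it would matter, and they do not imply that the readings are equally likely.

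**Step 5: both lists applied together.** The lists differ by omission, so a child who clears both breaches neither. Child B is then excluded whichever way the Summary is read. Child A is still excluded on the broad reading and not on the narrow one. Combining the lists settles the omission but not the ambiguity.

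**Step 6: how many children?** That would need the frequency of past anaphylaxis among preschool children with wheeze and the number to be screened. The documents give neither. The target of 100 recruited children does not supply either figure, and no prevalence is assumed here.

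**The case against.** The strongest reply has three parts.

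First, the ambiguity may be overstated. Section 7.2.1 uses near-fatal asthma together with the ventilation clause as a single unit, with no anaphylaxis in the sentence. That suggests the clause belongs to asthma, so that the Summary means anaphylaxis of any kind or that unit. This is fair. It makes the broad reading the more natural one, but it does not settle the wording. It also leaves the conflict between the sections intact: on the broad reading they disagree about child A and child B alike.

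Second, divergent screening is possible but not shown. Section 7.1 gives the full screen to the principal investigator or a qualified delegate, and the record search in Section 6 only finds families to approach. No text shows different staff working from different lists. This limits the likely consequence. A single team can still use the wrong list, and nothing tells it which one to use.

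Third, the harm is contained. Sections 5.1 and 8.7 describe an allergic reaction as very improbable, staff are trained in managing one, and adrenaline and antihistamines are to hand. Section 7.3 lets the investigator withdraw a child to protect wellbeing. All of this stands and caps the weight of the point. But these provisions deal with a reaction if it occurs, or with a child already enrolled. They do not say who is eligible.

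**Conclusion.** The concern holds. The two child exclusion lists contradict each other on item 6, and the Summary's version does not make clear whether the ventilation qualifier applies to anaphylaxis. Section 7.2.1 on its own allows entry to children with past anaphylaxis whom the Summary excludes.

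The size in children cannot be estimated. The point concerns consistent eligibility and participant safety, with no effect claimed on outcomes, analysis or sample size. It should be fixed, but it does not threaten the study.

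The conclusion rests on the two eligibility sections, both of which can be read in full on this item. The title pages, the Section 3 flowchart, the text between Appendix 1's procedures table and Appendix 2, and the case report form were not available. If one of them states a governing list, that would resolve which list applies, but the two sections would still need to agree.

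**What to change.** Reconcile the Study Summary and Section 7.2.1 so that exclusion 6 reads identically in both. The single wording should state whether a history of anaphylaxis excludes a child and, if so, whether the ventilation qualifier applies to it. Writing the two conditions as separate items would remove the grammatical doubt. The investigators decide which rule is clinically right; none is proposed here.

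Use the agreed wording wherever the criteria are applied: the Emergency Department record search (Section 6), the full screen (Section 7.1) and the eligibility check in Appendix 1.

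The cost is a short text change and reissue to the sites in Table 1 of Appendix 1. Because it touches an eligibility criterion, it is assumed to need sponsor and ethics/HRA review; the protocol does not set out the route for such a text change. Sample size, visits and tests are unaffected.

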7.2.2. HEALTHCARE PROFESSIONALS

INCLUSION CRITERIA	EXCLUSION CRITERIA

1. Doctors and nurses working in GP practices.
	
1. Inability to understand and cooperate with study procedures.

7.3. WITHDRAWAL CRITERIA

Parents can withdraw their child at any time without having to justify their decision. Upon withdrawal, patients will continue in their usual clinical care. In addition, the investigator may withdraw a child participant from the study if it is considered necessary to protect their wellbeing or that of others. Child participants' data will be retained and included in the final study analysis, unless the parent/carer specifies otherwise. Reasons for withdrawal, where available, and timing of withdrawal will be collected and recorded. Attempts to replace child participants whose parents decided to withdraw, will be made in line with recruitment procedures outlined in section 4. If the child participant is withdrawn due to an adverse event, the research team will

arrange for follow-up visits or telephone calls to monitor the adverse event until it has resolved or stabilised.

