6.1. STUDY OUTCOME MEASURES

Primary outcome:

Acute attacks of wheeze defined as requiring an unscheduled health care visit

Secondary outcomes:

- Carer days off work
- Days the child unable to attend childcare facility
- Use of oral corticosteroids
- Use of inhaled β -2 agonist (rescue therapy)
- Assessment if children's respiratory or wheezing condition is under control by using the TRACK™ score questionnaire (Test for Respiratory and Asthma Control in Kids) (Appendix 3).

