11. STATISTICS AND DATA ANALYSIS

The statistical analysis of the project will be done by [name] in collaboration with [name] (University of Edinburgh) and the Asthma UK Centre for Applied Research (AUKCAR), the funder of the study. Statistical analyses will use the GraphPad PRISM software package. A normality test will be performed to assess normal (Gaussian) distribution (e.g., the Shapiro-Wilk test. If there is normal distribution, then parametric tests will be used, otherwise non-parametric tests. Level of significance is set as a p value <0.05. The tests that are currently planned to be used are:

- **Chi-Squared test (x²-test)**

This test allows assessing if a variable is similar between two or more groups or to test if two or more variables are related/dependent

- **Fisher's Exact test**

This test is used when chi-squared values are <5, usually with a small sample size.

- **Student t-test or Mann-Whitney test**

These tests are used for comparison between two study groups. The first is for normally distributed quantitative variables and the second for non-normally distributed quantitative variables.

Data and all appropriate documentation will be stored for a minimum of 10 years after the completion of the study, including the follow-up period.

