13.5. DIRECT ACCESS TO SOURCE DATA

The Investigator(s)/institution will permit study-related monitoring, audits, REC review, and regulatory inspection(s), providing direct access to source data/documents. Parents will be informed of this during the informed consent discussion. Parents will be asked to consent to provide access to their medical notes.

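### Withdrawn children stay in the final analysis, but none of the listed tests accounts for length of follow-up, so early leavers are under-counted for the primary outcome

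*Combined protocol and SAP*

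**What the plan says.** On withdrawal, Section 7.3 states: "Child participants' data will be retained and included in the final study analysis, unless the parent/carer specifies otherwise". Of care afterwards it says: "Upon withdrawal, patients will continue in their usual clinical care". The only later study contact it describes is for one kind of withdrawal ("If the child participant is withdrawn due to an adverse event, the research team will" arrange monitoring until the event settles). It also provides that "Reasons for withdrawal, where available, and timing of withdrawal will be collected and recorded", and that withdrawn children may be replaced: "Attempts to replace child participants whose parents decided to withdraw, will be made in line with recruitment procedures outlined in section 4".

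The primary outcome in Section 6.1 is "Acute attacks of wheeze defined as requiring an unscheduled health care visit". Neither that section nor Section 11 says whether it is analysed as any versus none, a count or a rate. It is collected by monthly parent questionnaire over 12 months (Section 9, Appendices 2 and 4).

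Section 11 lists the tests currently planned: chi-squared or Fisher's exact for categorical variables, and Student's t or Mann-Whitney for quantitative ones. Of the last pair it says: "These tests are used for comparison between two study groups". It names no person-time, censoring or missing-data method. Section 13.5, on monitoring and audit, adds: "Parents will be asked to consent to provide access to their medical notes".

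**The concern.** The listed tests take one value per child. A child seen for 2 months without an attack has the value 'no', or a count of 0, exactly like a child seen for 12 months without one. Leaving that child out would go against Section 7.3. The timing of withdrawal is recorded, but no planned analysis uses it.

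Two uses of the data are affected. Section 4.3 wants pilot data for the power calculation of a later trial, and an attack risk that treats part-year children as full-year children is too low for that purpose. Section 5 asks whether the biomarkers predict attacks. If families of biomarker-negative and biomarker-positive children leave at different rates, the groups differ in time observed, and the listed tests read that as a difference in attacks.

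**Working it through.** The plan has no figure to reproduce: the target of 100 children comes without a power, attack-rate or dropout assumption. The size of the effect therefore has to be illustrated.

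**From the documents:** 12 months of follow-up per child (Section 10), significance at p < 0.05 (Section 11; sidedness not stated), 100 children (Section 5).

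**Assumed:** attacks follow a Poisson process at rate r per year (0.5, 1 or 2); leavers' exit times are uniform over the year; withdrawal w is between 0 and 40%.

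**Chance of at least one recorded attack**
- Full follow-up: 1 − e^(−r). At r = 1 this is 0.632.
- Leaver with uniform exit time: 1 − (1 − e^(−r))/r. At r = 1 this is 0.368.
- Exit at exactly 3 or 6 months, r = 1: 1 − e^(−0.25) = 0.221 and 1 − e^(−0.5) = 0.393.
- The full-follow-up and leaver figures are 39% and 21% at r = 0.5, and 86% and 57% at r = 2.

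**Overall recorded risk at r = 1:** (1 − w) × 0.632 + w × 0.368
- w = 20%: 0.579, against 0.632 with complete follow-up.
- w = 10%: 0.606.
- w = 30%: 0.553.

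**Two groups with the same true rate:** with 30% leaving in one and 10% in the other, the recorded risks are 55% and 61%. Mean counts are r × (1 − w/2), so their ratio is 0.95/0.85 = 1.12 when the true ratio is 1.

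**False-positive error** (4,000 simulated studies per setting, 50 versus 50 children, two-sided 0.05, r = 1 and 2):

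| Withdrawal | Chi-squared or Mann-Whitney | Rate comparison using observed time |
|---|---|---|
| 0% or 20% in both groups | 4.4% to 5.7% | 4.9% to 5.4% |
| 10% vs 30% | 8.6% to 11.9% | 4.7% to 5.5% |
| 0% vs 40% | 20% to 33% | 4.8% to 5.3% |

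**Power when the true rates are 1 and 2 per year**

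| Withdrawal (low-rate, high-rate group) | Chi-squared | Mann-Whitney | Rate comparison |
|---|---|---|---|
| 0%, 0% | 78% | 98% | 99% |
| 20%, 20% | 70% | 94% | 98% |
| 10%, 30% | 45% | 81% | 97% |

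Equal withdrawal therefore lowers the recorded risk and costs power, but leaves the false-positive rate near 5%. Unequal withdrawal is what distorts the comparison. The simulated rate comparison uses exact counts and exit times independent of attacks. It shows what is gained by using observed time; the first-event analysis proposed under the fix was not itself simulated.

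**The case against.** The strongest reply is that the plan is silent rather than wrong. It does not say that unobserved months count as attack-free. The outcome variable is undefined, so a t-test or Mann-Whitney test could be run on attacks per observed month. The test list is provisional, and the recorded timing of withdrawal would support a better analysis. All of that is true, but no such variable or method is named. With the listed tests applied to any-versus-none or to counts, the under-counting follows without anyone entering zeros for missing months.

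The end of outcome collection is also an inference. Section 7.3 does not state it, and Section 13.5 mentions access to notes. That access is framed as monitoring and audit, however, and no section continues the questionnaires or searches the notes after withdrawal.

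The illustrated shifts are modest for a feasibility study. At a risk of 0.632, a proportion in 100 children has a 95% margin of 1.96 × √(0.632 × 0.368/100), about 9.5 points, against a shift of about 5. The spurious differences need a 3:1 or greater imbalance in withdrawal, for which the documents give no figure. Replacement dilutes the effect a little: if 20 of 100 leave and 20 full followers are added, leavers are 20/120 = 16.7%, and the recorded risk is 0.632 − 0.167 × 0.264 = 0.588. These points limit the size. They do not remove the bias, and a larger sample would not remove it either.

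A reader might also infer that every early leaver looks attack-free. That goes too far: attacks before withdrawal are kept, and under the assumptions above 37% of leavers still show one.

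**Conclusion.** The point holds. Withdrawn children are analysed, no outcome collection after withdrawal is described, and none of the listed tests accounts for length of follow-up. Leavers are under-counted, and those with no attack so far are treated like children who were attack-free for 12 months. At 1 attack per year, uniform exit times and 20% withdrawal, the recorded risk is 58% instead of 63%. With 30% versus 10% withdrawal and no true difference, it is 55% versus 61%. The attack and withdrawal rates are assumptions, and the second result needs withdrawal to differ by biomarker group.

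It is tempting to conclude that the biomarkers will look more predictive than they are, because Section 4.3 says children without positive tests rarely have attacks and their families might lose interest. The documents do not support a direction. Families of sicker children may leave instead, and Section 7.3 lets the investigator withdraw a child to protect wellbeing. If more biomarker-positive children leave, a true association is diluted. The change should be made because the better method is cheap and the study's main comparison depends on it.

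**What to change.** **In Section 11:**
- Define the primary analysis as time to the first month with an unscheduled wheeze visit, by biomarker group, using Kaplan-Meier with log-rank or Cox, or a discrete-time equivalent.
- Censor at the last month covered by a returned monthly questionnaire. Censoring at the withdrawal date would treat unanswered months before it as observed. State a rule for gaps between returned questionnaires, which raise the same problem.
- Report the 12-month attack risk from the Kaplan-Meier estimate.
- As an alternative, compare the number of months with an attack, with the number of questionnaire months returned as the offset. A true attack rate ratio is not available from the present form, because Question 3 in Appendix 4 records visits in bands and its lowest non-zero band covers one or two. It would have to ask for the number of visits.
- State that censoring assumes leaving is unrelated to attack risk within biomarker group, and add a sensitivity analysis. One simple pair of bounds counts attack-free leavers first as having no attack and then as having one. In the 20% example this gives 0.579 and 0.8 × 0.632 + 0.2 = 0.706.

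**Optional:** where parents agree, count unscheduled wheeze visits from the medical notes to month 12. Section 7.3 already separates leaving the study from refusing use of data, so only this passive follow-up is new. The consent wording would have to go beyond the monitoring and audit access in Section 13.5, and notes would have to be searched at several practices and a hospital.

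**Cost:** a short paragraph in Section 11 and slightly more analysis than the listed tests. The core change needs no new data. The optional steps need a form or consent amendment.
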